3.3.3. Pharmacokinetics

Secondary Endpoints:

The data permitting the following plasma PK parameters will be evaluated after single and multiple dose administration for the extensive and sparse PK sampling groups:

- Maximum observed concentration (C_{max})
- Time corresponding to occurrence of C_{max} (t_{max})
- AUC from time zero to 24 hours (AUC₀₋₂₄)
- Apparent terminal elimination half-life $(t_{1/2})$
- Apparent clearance (CL/F)
- Apparent volume of distribution during terminal phase (V_z/F)
- Concentration immediately prior to dosing (C_{trough}). This parameter will only be calculated during the multiple dose administration.

4. STUDY DESIGN

4.1. Overview

This is a double-blind, randomized, placebo controlled, parallel group, dose ranging study to explore the efficacy, safety, tolerability and PK of 2 different doses of CPL500036 (PDE10A inhibitor) in patients with an acute exacerbation of schizophrenia when administered for 28 days.

The study will be conducted at multiple clinical units. Approximately 165 patients will be randomized at a 1:1:1 ratio to receive 20 mg CPL500036, 40 mg CPL500036 or placebo.

The study will comprise of a Screening Period (that will include a prior Medication Washout Period), a Treatment Period and a Follow-up Period.

For the Screening Period, patients will undergo screening assessments from Day -10 to Day -8 in multiple settings (i.e., emergency departments, outpatient clinics, etc.). Rolling admission will be employed in this study. Patients that fulfil all the inclusion criteria and none of the exclusion criteria will immediately be admitted to the Clinical Unit and enter a Medication Washout Period of up to 7 days (Day -7 to Day -1) before the randomization on Day 0. The duration of the Medication Washout Period may be shorter or omitted for non-medicated patients.

During the Treatment Period, patients will be dosed with 20 mg CPL500036, 40 mg CPL500036 or placebo once daily for 28 consecutive days (Day 1 to Day 28). Patients will remain in-house for the duration of the Treatment Period.

Approximately 30% of the patients (17 patients in each of the 3 treatment groups) will undergo extensive PK sampling during the Treatment Period, and the remaining 70% of the patients will only undergo sparse PK sampling.

On Day 29, the patients may resume anti-psychotics treatment. The Investigator will continue to monitor the patient for safety and clinical stability. Patients will be discharged from the Clinical Unit based on local standards of care if the patient is in a stable condition under the regular medication(s).

After discharge from the Clinical Unit, patients will return to the Clinical Unit for 2 once weekly Follow-up Visits, $7 (\pm 1)$ and $14 (\pm 1)$ days after the last dose of the investigational medicinal product (IMP) (Day 35 and Day 42).

Patients that withdraw or are withdrawn from the study will attend an early termination visit at the Clinical Unit and 2 safety Follow-up Visits 7 (\pm 1) and 14 (\pm 1) days after the last dose of IMP.

4.2. Scientific Rationale for the Study Design

This study evaluates the efficacy, safety, tolerability and PK of 2 different doses of CPL500036 (PDE10A inhibitor) in patients with an acute exacerbation of schizophrenia. The design is standard and is considered appropriate to meet the objectives of the study.

The study design meets the recommendations provided in the "Guideline on clinical investigation of medicinal products, including depot preparations in the treatment of schizophrenia" (EMA/CHMP/40072/2010 Rev. 1, 30). This is a proof-of-concept study assessing CPL500036 compound with new mechanism of action in treating positive symptoms of schizophrenia so comparison to placebo is considered appropriate to assess treatment benefit. To better characterize the effect size two doses of CPL500036 as monotherapy will be used. Risks in the study, especially those of using placebo were acknowledge and the study was design to minimize it (see section 2.5). For efficacy assessment validated scales recommended in the guideline are to be used as an assessment tools. PANSS will be used for primary endpoint measurements, including the recommended definition of responders used in short term trials with acute/exacerbated symptoms is to be used for clinical response evaluation. For secondary efficacy measures both CGI-S and CGI-I assessments are planned in the study. Extrapyramidal symptoms (EPS) are potential adverse events that according to guideline are to be monitored during the studies in schizophrenia patients, which was addressed by using ESRS scale for EPS monitoring.

The safety assessments for the study are accepted measures for ensuring safety of subjects during a clinical trial. The PK sampling schedule is considered appropriate given the information available. The rationale for dose selection is discussed in Section 4.3.

4.3. Justification for Dose

4.4. Order of Assessments

The following priority order will be in effect when more than one assessment is required at a pre-dose and post-dose time point, with PK blood sampling being performed in the specified time:

1. Vital signs,

- 2. 12-lead ECG,
- 3. Blood sampling for safety and PK assessments,
- 4. PANSS, CGI-S, CGI-I and BACS,
- 5. ESRS monitoring,
- 6. Columbia Suicide Severity Rating Scale (C-SSRS).

4.5. Study Duration

The duration of participation for each subject will be approximately 8 weeks. The estimated study duration includes:

- 7. Screening Period: Up to 10 days.
- 8. Treatment Period: Days 1 to 28.
- 9. Follow-up Period: 7 to 14 days after the post-last dose of IMP (Day 28) Days 35 to 42.

4.6. End of the Study

For the entire study, end of the study is defined as the last visit of the last subject for any protocol related activity (last subject, last visit). -

4.7. Study Completion

A subject is to be considered to have completed the double-blind treatment phase if he/she has completed all the assessments and procedures on Day 28. Subject who, for any reason, discontinues the study before Day 28 is not to be considered to have completed the study.

4.8. Early Termination

If a subject withdraws prematurely after dosing, all data normally collected at discharge from the clinical site should be collected at the time of premature discontinuation or at the scheduled discharge. If deemed necessary by the Investigator, the subject will be asked to return for an unscheduled visit for safety follow-up.

5. STUDY POPULATION

The study population will consist of male and female patients with an acute exacerbation of schizophrenia. Subjects must be able to provide written informed consent and meet all the inclusion criteria and none of the exclusion criteria.

NOTE: Investigators should ensure that all study enrollment criteria have been met at screening and on Day -1. If a patient status after screening changes at baseline (Day -1) such that the study patient no longer meets all eligibility criteria, then the patient should be excluded from participation in the study (such patient is to be considered as screen failure). It should be remembered that all baseline procedures must be performed on Day -1, but final patient qualification should be made when all results are available, before randomization on Day 0.

5.1. Number of Subjects

A total of 165 subjects will be enrolled in the clinical study.

5.2. Inclusion Criteria

Patients eligible for inclusion in this study have to fulfil all of the following criteria:

- 1. The patient has a primary diagnosis of schizophrenia (Diagnostic and Statistical Manual of Mental Disorders, 5th Edition [DSM-5], 295.90) confirmed by clinical interview (Structured Clinical Interview for DSM-5 Clinical Trial Version [SCID-5-CT]). The participant's initial diagnosis must be greater than or equal to (≥) 2 year before Screening.
- 2. Male or female patient aged 18 to 65, inclusive, at Screening.
- 3. The patient's psychotic symptoms were exacerbated within 2 months (60 days) prior to Screening (e.g., aggravated delusion).
- 4. The patient has a score of 5 (moderate severe) or higher in 3 or more items of the following PANSS items at Screening and Day -1: delusions (P1), conceptual disorganization (P2), hallucinations (P3), suspiciousness (P6), and unusual thought content (G9).
- 5. The patient has a PANSS Total Score of 80 or higher during Screening and on Day -1.
- 6. A female is eligible to participate if she is not pregnant (negative pregnancy test at Screening and Day -1), not breastfeeding, and at least 1 of the following conditions applies:
 - a) Not a woman of childbearing potential (a woman is considered to be of non-childbearing potential if she is post-menopausal for at least 12 months or is surgically sterile [hysterectomy, bilateral oophorectomy, tubal ligation]).

- b) Woman of childbearing potential, who agree to use contraceptive methods during the Treatment Period and for at least 28 days after the last dose of the study drug. The following are acceptable contraceptive methods: bilateral tubal occlusion, male sterilization, established proper use of hormonal contraceptives that inhibit ovulation, hormone-releasing intrauterine devices and copper intrauterine devices, male or female condom with spermicide; and cap, diaphragm, or sponge with spermicide.
- 7. Male patients must agree to use a barrier method of contraceptive (condom + spermicide gel) for at least 90 days after the last dose of the study drug.
- 8. The patient has a Clinical Global Impression Scale- Severity of Illness Scale (CGI-S) of 4 or greater at Screening and Day -1.
- 9. The patient is able to and agrees to remain off prior antipsychotic medication and all excluded medications as outlined in the protocol for the duration of the Treatment Period.
- 10. The patient is able to sign informed consent after receiving information about the trial.
- 11. The patient has the ability and willingness to comply with the requirements and restrictions of the study protocol.

5.3. Exclusion Criteria

Patients eligible for inclusion in this study must **not** fulfil any of the following criteria:

- The patient has a decrease in the PANSS Total Score by 20 percent (%) or more at Baseline (Day -1) compared with the Total Score at Screening ([PANSS Total Score at Screening PANSS Total Score at Baseline]/[PANSS Total Score at Screening- 30)]*100 ≥ 20%).
- 2. Patient participated in another interventional clinical study with an IMP during the last 30 days or 5 half-lives, whichever is longer, prior to the first dose of study drug.
- 3. The patient has uncontrolled, hypertension, hypotension, clinically significant neurologic, cardiovascular, pulmonary, hepatic, renal, metabolic, gastrointestinal, or endocrine disease or other abnormality (other than the disease being studied), which may impact the ability of the patient to participate or potentially confound the study results.
- 4. The patient has a history of severe head injury, traumatic brain injury, myocardial infarction or stroke.
- 5. The patient has a positive urine drug result (illicit, illegal or without valid prescription or medical need) at Screening.

- 6. The patient has a moderate or severe substance use disorder (meeting more than 4 diagnostic criteria of DSM-5 either currently or within the last 6 months) for alcohol or other substances of abuse except nicotine or caffeine.
- 7. If female, the patient is pregnant (a positive pregnancy test at Screening or Day -1) or lactating or intending to become pregnant or intending to donate ova, before or during the course of the study or within 12 weeks after the last dose.
- 8. The patient has a history of or known personality disorder or other psychiatric disorder that, in the opinion of the Investigator, would interfere with participation in the study.
- 9. The patient has a history of neuroleptic malignant syndrome, water intoxication, or paralytic ileus or other conditions that may interfere with absorption of study drug.
- 10. The patient is considered by the Investigator to be at imminent risk of suicide or injury to self, others, or property or participants who within the past year prior to Screening have attempted suicide or have positive answers on item 4 or 5 on the C-SSRS at Screening or on Day -1.
- 11. The patient has Parkinson's disease, tardive dyskinesia, or other chronic movement disorder that may interfere with the interpretation of study results.
- 12. The patient has any existing or previous history of cancer that has been in remission for less than 5 years prior to Screening.
 - Note: this criterion does not include those participants with basal cell, stage I squamous cell skin cancer or in situ cervical cancer.
- 13. The patient has newly diagnosed diabetes or requires insulin for their treatment; diabetic patients that have had changes to their diabetic treatment regimen within 30 days prior to Screening or diabetic patients that have been hospitalized for their diabetes and/or diabetes related conditions in the past year prior to Screening.
- 14. The patient has long QT syndrome or is under treatment with Class 1A (e.g., quinidine, procainamide) or Class 3 (e.g., amiodarone, sotalol) anti-arrhythmic drugs.
- 15. The patient with acute or chronic hepatitis B or C infection (positive test for hepatitis B surface antigen; positive hepatitis C antibody), known human immunodeficiency virus (HIV) infection, or other acute or ongoing clinically significant viral or bacterial infections..
- 16. The patient has received any depot preparation (sustained-release formulation) of antipsychotic drugs within 1 month (30 days) prior to Screening.

- 17. The patient is considered to be treatment resistant. Treatment resistance is defined as prior non-response to 2 courses of treatment with anti-psychotics of different chemical classes for at least 4 weeks each at doses considered to be effective.
- 18. The patient has received monoamine oxidase (MAO) inhibitors or fluoxetine within 1 month (30 days) before Screening.
- 19. The patient has received electroconvulsive therapy within 6 months (180 days) before Screening.
- 20. The patient has 1 or more laboratory values outside the normal range that are considered by the Investigator to be clinically significant at Screening; or has any of the following at Screening:
 - A serum creatinine value > 1.5 times the upper limit of normal (ULN).
 - A total serum total bilirubin value > 1.5*ULN.
 - A serum alanine aminotransferase (ALT) or aspartate aminotransferase (AST) value > 2*ULN.

5.4. Restrictions

5.4.1. Dietary and Fluid Restrictions

Caffeine

Xanthine containing products (e.g., caffeine in coffee, tea, chocolate) will not be allowed from 24 hours prior to Day 1 to Day 28, inclusive. Subjects should not consume caffeine containing beverages exceeding 500 mg caffeine per day (5 cups of coffee) during the off-site days during the study.

Alcohol

Consumption of alcohol and alcohol-containing foods, medications or beverages must be avoided from 48 hours prior to Day -1 and while subjects are confined to the study center. Subjects should not consume more than 3 units (males) or 2 units (females) per day during the study Follow-up period (1 unit is equal to approximately ½ pint [284 mL] of beer, one small glass [125 mL] of wine, or one measure [25 mL] of spirits).

Meals

No outside food or drink is permitted at the study center. During in-house stay at the study center only meals and fluid intake according to the study center's meal plan will be allowed.

Fasting

Dosing Day: Dosing during treatment period will take place after an overnight fast of at least 10 hours. Water intake will be allowed up to 1 hour before dosing and from 1 hour after dosing (excluding amount of water allowed for IMP administration).

After IMP administration patients should remain fasting:

- On Day 1, Days 2-6, Day 7 and Day 28: up to 2 hours,
- On every other day: up to 2h but starting from 0.5h after IMP administration consumption of low calorie snack i.e. plain rice cakes is allowed till breakfast.

5.4.2. Lifestyle Considerations

Drugs of abuse

Subjects must refrain from use of recreational drugs for the duration of the study.

Nicotine

Cigarette smokers will be allowed to smoke in designated areas provided by the clinic and the number of cigarettes per day should be recorded. The number of cigarettes will be limited to a maximum of 20 per day. No smoking will be allowed 90 minutes before efficacy testing.

Strenuous activity

Subjects should refrain from carrying out heavy physical training (e.g., long distance running, weight-lifting, or any physical activity to which the subject is not accustomed) from 48 hours prior to Day -7 – Day -1 (depending if/ how long washout period is included) until the final Follow-up Visit. Subjects should neither start any new physical training nor increase the intensity of their usual training during study participation. Subjects may participate in light recreational activities during studies (e.g., watch television, play computer games, read).

5.4.3. Prior and Concomitant Treatments

Medication restrictions applicable before dosing are described in Section 5.3 (exclusion criteria). Prior medication will be recorded.

Any medicinal product, prescribed or over-the-counter (OTC), taken by a subject other than the IMP, is considered concomitant medication. Permitted medication (for prolonged use) includes only paracetamol in recommended doses (≤ 2 g per day) after approval by the Investigator or designee. Higher doses of paracetamol, up to 4 g per day may be given at the discretion of the

Investigator or designee to treat AEs such as fever and headache (only for short terms issues). Any concomitant treatment will be given only if deemed strictly necessary by the Investigator or designee. Use of concomitant medication will be recorded and reported.

Allowed concomitant medications taken by the patient in fasting conditions can be taken consistently with the current recommendations, but at least 1 hour interval between concomitant medication and IMP administration must be maintained with IMP taken as first.

Starting on the first day of Screening Period and as applicable, all antipsychotic or other psychotropic medications will be stopped with clinically appropriate titration down as per Investigator clinical judgment. Thereafter, patients will be instructed not to take any medications during the conduct of the study unless approved by the Investigator. Any patient who is unable to be safely discontinued from current antipsychotic therapy or other psychotropic medications will not be eligible for the study (see Section 7).

Medication history (psychotropic medication history during the previous 5 years and all other medications during the past 12 months) will be recorded at Screening (Visit 1) in the eCRF. Thereafter, any changes in concomitant medications or new medications added will be recorded in the eCRF.

Patients will not be eligible for the study if they have used any depot antipsychotic within 1 month (30 days) prior to Screening. The using of mianserin, mirtazapine, nefazadone, cyproheptadine, or fluvoxamine within 1 month (30 days) before Screening is not recommended.

During the study lorazepam may be administered for anxiety/agitation or to aid sleep; from other medications to manage insomnia, known as z-drugs, zolpidem is preferred and allowed. Lorazepam and zolpidem are not to be used in close temporal proximity (administration within 4h of each other). In addition, benzatropine/biperiden may be administered for treatment of extrapyramidal side effects and propranolol may be administered for treatment of akathisia. Lorazepam, zolpidem, benzatropine/biperiden and propranolol are allowed according to the instructions outlined in Table 5 below. Within the daily and weekly limits shown in Table 5, lorazepam, zolpidem, benzatropine/biperiden, and propranolol are permitted upon the Investigator or designee decision and are allowed on a PRN (as needed) basis.

If the patient's condition will require administration of higher dose of lorazepam, zolpidem, benzatropine/biperiden, or propranolol (exceeding the limits given in Table 5), it must be recorded as Serious Adverse Event (SAE).

The adverse event (AE) associated with the need for lorazepam, zolpidem, benzatropine/biperiden, or propranolol should be recorded on the AE eCRF. The amount and timing of each lorazepam, zolpidem, benzatropine/biperiden, or propranolol administration should be recorded for each patient in the eCRF.

Table 5 Restrictions on the Use of Lorazepam, Zolpidem, Benzatropine/Biperiden, and Propranolol during the Study

Medication	Study Period	Dosage Allowed	Timing Restrictions
Lorazepam	Screening Period and Treatment Period to Day 28, inclusive	Maximum of 6 mg/day AND	Not within 8 hours prior to PANSS, CGI-S, CGI-I or C-SSRS, BACS Not within 4 h of zolpidem administration
		Maximum 6 times/week (at least 1 day break between weeks)	
	Follow up period – Since Day 29 and onwards	According to SmPC	
Zolpidem	Screening Period and Treatment Period to Day 28, inclusive	Maximum of 10 mg/day	Not within 8 hours prior to PANSS, CGI-S, CGI-I or C-SSRS, BACS Not within 4 h of lorazepam administration
		Maximum 4 times/week	
	Follow up period – Since Day 29 and onwards	According to SmPC	
Benzatropine	Screening Period to Day 28, inclusive	Maximum of 4 mg/day	Not within 8 hours of BACS, ESRS
Biperiden		According to SmPC	
Propranolol	Screening Period to Day 28, inclusive	Maximum of 40 mg/day	

BACS: Brief Assessment of Cognition in Schizophrenia; C-SSRS: Columbia Suicide Severity Rating Scale; CGI-I: Clinical Global Impression Scale - Improvement; CGI-S: Clinical Global Impression Scale - Severity; PANSS: Positive and Negative Syndrome Scale

A list of example medications that are allowed and not allowed as concomitant medications for either episodic or chronic use is provided in Table 9 in the Appendices (Section 13).

Strong inducers and inhibitors of CYP3A4 should be avoided due to possible effects on the pharmacokinetics of CPL500036 (PDE10A inhibitor), however, moderate to weak inducers or inhibitors may be allowed.

Precaution should be exercised in patients using concomitant treatment with agents being BCRP (Breast Cancer Resistance Protein) substrates (e.g. ezetimibe, pravastatin, rosuvastatin), as the Investigational Product may inhibit the BCRP. As per Table 9, the dose of these drugs should be stable within 1 month prior to Screening to allow objective patient's follow up. Any confusions related to the changes in patient's status and/or laboratory results should be discussed with the Medical Monitor.

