The 02PDE2019 study is considered a short term study with up to 7 days of medication washout period and 28-day treatment phase. The CPL500036 compound will be used in monotherapy, so other antipsychotic treatments will be discontinued, what is in line with the EMA guidelines which states that "treatments that may augment the test treatment should be excluded, despite the consequences of these exclusions for generalizability of the trial results. Therefore other antipsychotic drugs should be discontinued (...)" [30]. The protocol has been designed to minimize the risk to all research participants. This study will be performed in controlled settings, all patients will be hospitalized to assure patients safety. Subjects will be monitored to detect AEs during the study and followed appropriately to ensure resolution of AEs.

To manage potential side effects and symptoms that may occur, allowed treatments are described. During the study lorazepam may be administered for anxiety/agitation or to aid sleep. To manage insomnia from z-drugs, use of zolpidem is allowed in the study. To treat extrapyramidal side effects and akathisia benzatropine/biperiden and propanolol are permitted, respectively. The daily and weekly limits of those medications that can be used, on a PRN (as needed) basis are provided (rules for medication administration in Section 5.4.3). If a patient's condition will require to exceed the specified dose, it must be recorded as Serious Adverse Event.

During the whole study all the patients will be closely observed by the Investigator or appointed staff members to assure maximal safety. Safety is to be ensured by performing clinical assessments/ evaluations and clinical laboratory measurements/ evaluations. This includes i.a. monitoring of vital signs with 3-positional blood pressure and pulse measurements, ECG measurements and extrapyramidal side effects monitoring using Extrapyramidal Symptom Rating Scale (ESRS) assessments. Patients at imminent risk of suicide or injury to self, others, or property or participants who within the past year prior to screening have attempted suicide will be excluded from the study and risk of potential suicide ideations occurrence will be assessed during the study.

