8.7. Hospitalization

Patients are to be hospitalized after the screening qualification for washout period of up to 7 days (if necessary) before the start of the 28-day Treatment Period. Patients are to be hospitalized during the treatment period (Day 1 to Day 28). On Day 29 patients may be discharged from the clinical centre based on local standards of care if the patient is in stable condition under the regular medication(s).

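### Protocol 5.4.3 starts antipsychotic withdrawal on the first screening day, up to 3 days before the admission at which 4.1, 8.7 and 9.1 start a 7-day washout; the sections must be reconciled with each other and with the safeguard in 2.5

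*Protocol*

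**What the plan says.** Two parts of the current protocol say when existing antipsychotics are withdrawn.

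- **Protocol 5.4.3** ties withdrawal to the start of screening: "Starting on the first day of Screening Period and as applicable, all antipsychotic or other psychotropic medications will be stopped", by down-titration. The pace is left to the Investigator. A patient who cannot be taken off medication safely is ineligible, and the reader is sent to Section 7.
- **Protocol 4.1** places screening before admission: "patients will undergo screening assessments from Day -10 to Day -8 in multiple settings (i.e., emergency departments, outpatient clinics, etc." Patients who then meet all criteria "will immediately be admitted to the Clinical Unit and enter a Medication Washout Period of up to 7 days (Day -7 to Day -1)." The synopsis (1.1), Protocol 9.1 and SAP 2.3 give the same sequence.
- **Protocol 8.7** agrees with 4.1: "Patients are to be hospitalized after the screening qualification for washout period of up to 7 days", if a washout is needed.
- **Protocol 2.5** describes a washout of at most 7 days and names the safeguard: "all patients will be hospitalized to assure patients safety". It does not itself say on which day withdrawal begins.
- **Table 1, footnote a** (protocol and SAP) describes up to 3 days of screening as in-house, but in the same sentence places it in several kinds of setting.
- **Protocol 4.5** limits the Screening Period to 10 days and gives no setting.

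**The concern.** The first day of screening and the day of admission after qualification are different triggers, and a site can comply with one and not the other. A site working from 5.4.3 may begin withdrawing medication in a patient seen in an emergency department or outpatient clinic, before laboratory and serology results have settled eligibility. These patients are in acute exacerbation, with a PANSS Total Score of at least 80. Protocol 2.5 defends both the washout and the placebo arm by hospital supervision. If withdrawal starts earlier and elsewhere than 2.5 assumes, the risk-benefit statement does not describe what the protocol allows.

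A patient whose medication was stopped or tapered at screening and who then proves ineligible is classed as a screen failure. Neither document says what applies to the medication already withdrawn.

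**Working it through.** **Inputs**

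- Earliest screening day: Day -10 (Protocol 4.1, Table 1; the 10-day limit in 4.5 agrees).
- Screening assessments: Day -10 to Day -8 (Protocol 1.1, 4.1, 9.1; SAP 2.3).
- Washout after admission: Day -7 to Day -1 (the same sections).
- Randomization on Day 0 and first dose on Day 1 (Protocol 9.3, 9.4).

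**Formula.** Inclusive length = last day - first day + 1.

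**Reproducing the stated figure.** Washout: -1 - (-7) + 1 = 7 days, which matches the stated maximum.

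**Under the 5.4.3 trigger**

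- Screening window: -8 - (-10) + 1 = 3 days.
- Gap from first screening day to a Day -7 admission: -7 - (-10) = 3 days.
- Stopping, tapering and washout together, Day -10 to Day -1: -1 - (-10) + 1 = 10 days.
- Excess over the stated washout: 10 - 7 = 3 days.
- Counting through Day 0, the last day before first dose: 0 - (-10) + 1 = 11 days, against 0 - (-7) + 1 = 8 days.

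**Range.** Assuming admission on Day -7:

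| First screening day | Days before admission | Days to Day -1 |
|---|---|---|
| -10 | 3 | 10 |
| -9 | 2 | 9 |
| -8 | 1 | 8 |

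If a patient qualifies and is admitted on the day screening starts, the gap is zero.

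**Does other text settle it?**

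- Table 1 marks washout in a single column covering Day -10 to Day -2, which fits either reading.
- Footnote a points both ways: in-house, yet in multiple settings, which 4.1 says include outpatient clinics.
- Protocol 5.4.2 ties washout to Day -7 to Day -1, in line with 4.1.
- Section 7, to which 5.4.3 refers, has no rule for a patient who cannot be safely discontinued before dosing. Section 7.1.1.1 opens with the period after the first dose. Section 7.2 provides only for replacing a patient found ineligible before dosing. Section 4.8 also concerns withdrawal after dosing.

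**The case against.** The strongest reply is that the texts are partly compatible. Protocol 5.4.3 speaks of down-titration, applies only where relevant and defers to clinical judgment. A taper could begin at screening and be followed by the 7-day inpatient washout, and 4.1 itself counts washout as part of the Screening Period. Footnote a calls screening in-house. Admission is rolling and immediate, patients who cannot be safely discontinued are ineligible, and Table 5 permits lorazepam and zolpidem within limits during screening.

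Much of this stands, and it rules out several stronger readings that a reader might infer:

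- **That patients are medication-free outside hospital for 3 days, or for 10 days in all.** This would require abrupt cessation on Day -10 and admission no earlier than Day -7. A tapering patient is still on drug, and footnote a leaves the screening setting unresolved.
- **That every medicated screen failure is affected.** Investigator judgment and the conditional wording of 5.4.3 do not support this.
- **That 2.5 itself fixes the start of washout at admission.** It gives a length and a safeguard; the sequence comes from 1.1, 4.1, 8.7 and 9.1.
- **That the discrepancy biases the treatment comparison, or shifts baseline severity or the number excluded for a PANSS fall of 20% or more.** Withdrawal precedes randomization, which is stratified by baseline PANSS, and the primary model adjusts for site and baseline score. The documents give no figures from which an effect on baseline or on exclusions could be sized.

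The reply does not remove the conflict over the trigger. None of 1.1, 4.1, 8.7 or 9.1 mentions a taper before admission, and 5.4.3 does not make withdrawal wait for qualification.

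**Conclusion.** The inconsistency is real and is in current operative text. Followed as written, 5.4.3 lets stopping or tapering begin up to 3 days before admission and before eligibility is known, and lets the whole process span up to 10 days against the 7 stated. Both figures assume a Day -10 start and a Day -7 admission. How many patients would be affected cannot be estimated: the documents give neither the screen-failure rate nor the proportion medicated at screening.

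The point concerns patient safety and the coherence of the risk-benefit case, not the validity of the treatment comparison. It merits correction because a compliant site could act outside the supervision on which 2.5 relies, and because neither Section 7 nor any other section covers the patient who is stopped or tapered and then fails screening.

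**What to change.** Reconcile Protocol 5.4.3 with Protocol 1.1, 2.5, 4.1, 8.7, 9.1 and Table 1 footnote a, and with SAP 2.3 and its copy of the footnote. One trigger, one setting and one maximum duration for antipsychotic discontinuation should be stated identically in all of them and should agree with the safeguard described in 2.5. Which timing or clinical rule is right is for the sponsor.

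In the same amendment:

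- Replace the 5.4.3 reference to Section 7 with one that leads to an applicable provision.
- Have the sponsor state what applies to a patient whose medication was stopped or tapered and who then fails screening.

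For reporting, summarise the time from last antipsychotic dose to baseline by arm. This needs no new collection: 5.4.3 already requires psychotropic history and medication changes in the eCRF, Protocol 10.9 lists start date and duration, and SAP 4.5 lists the date of last administration where known.

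The cost is a wording amendment, a site notification and one descriptive table, with no added procedure or patient. If enrolment has already finished, which the documents do not say, the clinical study report should describe what sites actually did.
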